3 PROTOCOL AMENDMENT

Applicable Section(s) Page(s)	Original text	New / revised text	Reason for change
Protocol version N° 1 –			
Protocol Amendment N° 1 –			

6 ABBREVIATIONS - DEFINITIONS

AE	Adverse Event
AUC	Area Under the Curve
CRA	Clinical Research Associate (synonym: monitor)
CRF	Case Report Form
CPM	Clinical Project Manager
DIAAS	Digestible Indispensable Amino Acids Score
GCP	Good Clinical Practice
IAA	Indispensable Amino Acids
IEC	Independent Ethics Committee
IRB	Institutional Review Board
ITT	Intent-To-Treat
MP	Method and Procedure: providing all the information necessary to carry out activities efficiently, safely, and in an authorized manner.
NB	Net Protein Balance (protein synthesis minus protein degradation)
PD	Protein Degradation (i.e., protein breakdown)
PP	Per-Protocol
PS	Protein Synthesis
SAE	Serious Adverse Event
SOP	Standard Operating Procedure: (Providing all the information necessary to use equipment efficiently, safely, and in an authorized manner)
SUSAR	Serious Unexpected Suspected Adverse Reaction (see definition in chapter 19.4.)
SMF	Study Master File

7 SYNOPSIS

An innovative development in nutrition involves assessing dietary protein quality through the Digestible Indispensable Amino Acid Score (DIAAS). Compared to the traditional Protein Digestibility Corrected Amino Acid Score (PDCAAS), the DIAAS offers a more accurate approach to assessing dietary protein quality (FAO, 2013). The DIAAS is based on measuring the true ileal digestibility of each indispensable amino acid (IAA) using growing pig digesta model, which has been confirmed to predict human digestibility (Hodgkinson et al., 2022). It eliminates truncation of the protein quality score, allowing for a more accurate ranking system to identify dietary protein quality and complementarity within protein sources (Moughan, 2019; Bailey et al., 2019). The ratio between the first limiting IAA in a test protein with the corresponding IAA in a reference protein defines the DIAAS. The DIAAS score can be classified into one of three quality categories: <75 (no quality), 75-99 (high-quality), and ≥ 100 (excellent quality). A DIAAS score of ≥ 100 implies that the dietary protein source is effectively utilized and satisfies the estimated average requirement for protein (EAR: 0.66 g kg⁻¹ d⁻¹). However, the effect of DIAAS on whole-body protein turnover has yet to be verified in detail.

To answer the question of the influence of protein quality measured by the DIAAS on whole-body protein turnover and the efficacy potential of combinatorial proteins in a whole-foods matrix, we will conduct a nutritional crossover study to compare how incremental increases in protein quality, as defined by the FAO DIAAS criteria: 50% (no quality), 75% (high-quality), and $\geq 100\%$ (excellent quality) affects protein kinetics in older men and women aged 67-77 years.

The study will compare 3 dietary protein interventions increasing in the DIAAS. The conditions will comprise meals with stepwise increases in DIAAS: 50%, 75%, and 100%. The protein-rich meals will be ingested orally on-site and be isocaloric (see Section 13.1). To measure splanchnic extraction, each meal will include oral ingestion of 84 mg of L-[¹⁵N]-Phenylalanine (ingested with the juice). Administration and sampling will occur in an air-conditioned clinic room after an overnight fast between 7:00 and 9:00 am. The participants will follow a controlled dinner the evening before the interventional days. Infusion of stable isotopes L-[Ring-²H₅]-Phenylalanine (Phe) and L-[Ring-²H₂]-Tyrosine (Tyr) will be administered over 5.5 hours to measure postprandial protein synthesis, breakdown, and protein net balance over 4 hours. Arterialized-venous blood will be collected from a hand vein at specified intervals for 5.5 hours (post-absorption and post-prandial) based on prior infusion studies.

Participants will remain rested during sampling and may do computer work, watch TV, or relax. There will be a minimum 1-week washout between trials. The 4-hour post-prandial response will be calculated as the area under the curve (AUC) using the post-absorptive concentration as the baseline reference. The AUC will then be divided by time to determine the average increase in post-prandial plasma concentration. We will calculate the whole-body PS, PB, and NB (NB = PS - PB) using the standard steady-state isotope dilution equations (Jonker et al., 2019). Outcomes will be analysed using mixed model analysis of variance (SAS, Cary, NC). Fixed effects will be meal condition and time (where relevant). Random effects will be subject to an unstructured covariance matrix to account for correlated data within the crossover. Data will be log-transform to improve linearity and model fit and to express outcomes as percent differences. Primary outcomes (PS, PB, and NB) will be referenced to our estimate of the smallest important clinical changes. Data will be presented as the least-squares mean and uncertainty (confidence interval) and, where useful, the effect size as a standardized mean difference with modified Cohen d effect size descriptors for the mean and breadth of the confidence interval. Results will be used to determine the influence of protein quality in a whole-food matrix defined by DIAAS and the effect of combining proteins to modify DIAAS on the primary health outcome of whole-body protein net balance governing lean mass homeostasis in older adults.

8 STUDY PLAN OVERVIEW

Days		1	8	15
		↑	↑	↑
Visits	0	1	2	3
	Recruitment	Test days		

Study plan showing the four visits to the lab. Days 1 through 15 assume weekly testing for men and women.

9 INTRODUCTION

In recent years, there has been a growing interest in shifting global protein consumption towards more sustainable food production based on the assumption that animal protein production impacts the environment significantly (Espinosa-Marrón et al., 2022). However, reducing dietary proteins from animal sources could potentially lower the protein quality of most diets, which is of crucial concern, given the vital role of dietary protein in human growth, maintenance, and physiological function (Wu, 2016). Unlike other macronutrients, dietary protein comprises all the nitrogen and amino acids required for synthesizing muscles and organs, the production of enzymes and hormones, and the functioning of the immune system (Wu, 2009).

Amino acids can be categorized as dispensable (DAAs) or indispensable amino acids (IAAs) based on their ability to be synthesized *de novo* in the body. Only DAAs can be synthesized effectively in humans, and IAAs must be obtained through dietary protein sources. In this context, assessing dietary protein quality should be based on the digestibility, absorbability, and bioavailability of IAAs. An innovative development in nutrition involves assessing dietary protein quality is through the Digestible Indispensable Amino Acid Score (DIAAS). Compared to the traditional Protein Digestibility Corrected Amino Acid Score (PDCAAS), the DIAAS offers a more accurate approach to assessing dietary protein quality (FAO, 2013). The DIAAS is based on measuring the true ileal digestibility of each amino acid using growing pig digesta, which has been confirmed to predict human digestibility (Hodgkinson et al., 2022). It eliminates truncation of the protein quality score, allowing for a more accurate ranking system to identify dietary protein quality and complementarity (Moughan, 2019; Bailey et al., 2019). The ratio between the first limiting IAA (LimAA) in a test protein with the corresponding IAA in a reference protein derives from the DIAAS. The DIAAS score can be classified into one of three quality categories: <75 (no quality), 75-99 (high-quality), and ≥ 100 (excellent quality). A DIAAS score of ≥ 100 implies that the dietary protein source is effectively utilized and satisfies the estimated average requirement for protein (EAR: 0.66 g kg⁻¹ d⁻¹).

It has been shown that higher-quality proteins (beef sirloin, pork loin, eggs) induce a greater increase in whole-body protein balance compared to lower-quality proteins (tofu, kidney beans, peanut butter, mixed nuts) due to greater IAA availability (Park et al., 2021). Even when consumed isocaloric (500 kcal) and isonitrogenous (26g protein from eggs and cereal) (Kim et al., 2018). However, these findings did not account for equal amounts of IAAs content. These differences in protein turnover can be attributed to limiting IAAs in lower-quality proteins, as indicated by their DIAAS values, which have been shown in cell cultures to decrease global rates of protein synthesis (Vaughan et al., 1971; van Venrooij et al., 1972; Pain & Henshaw, 1975). In addition, since the limiting amino acid also limits the use of all other dietary amino acids for protein synthesis, the body must oxidize excess amounts of these amino acids (Bos et al., 2003; Tujioka et al., 2011; Luiking et al., 2005). In contrast, if one increases the dietary amount of the first limiting amino acid, protein synthesis will increase, and so will the utilization of the other dietary amino acids, reducing their oxidation (Gorissen et al., 2016). These findings align with recent research indicating that elevated peripheral levels of IAAs are linked to enhanced muscle and whole-body protein synthesis, especially following meals (Church et al., 2020). Once the limiting amino acid requirement is reached, further increases in dietary intake will cause no further increase in protein synthesis nor a decrease in the oxidation of the other IAAs (Gaudichon & Calvez, 2021; FAO, 2007). Despite our growing understanding of protein quality and advancements in measuring dietary protein quality through the DIAAS, the relationship between the DIAAS and protein turnover has yet to be verified in humans. This knowledge gap is significant as dietary protein is crucial for

maintaining health, preventing disease, and mitigating protein malnutrition (Manary et al., 2016; Layman et al., 2008).

Integrating the DIAAS is paramount for the aging population, as progressive loss of muscle mass, strength, and function, strongly predicts disability and mortality in older adults aged 50-86 (Su et al., 2022; Xu et al., 2021). Slowing or preventing the progression of sarcopenia is of utmost importance for maintaining or improving the quality of life for older adults. It is well established that dietary protein intake stimulates an anabolic response (Volpi et al., 2003; Wolfe et al., 2008) mainly via stimulating protein synthesis by IAAs, which is predominantly blunted in older adults. Hence, the importance of the DIAAS could prove valuable to ensure optimal IAA intake for older adults to support skeletal muscle mass retention and whole-body protein net balance. However, the relationship between the calculated DIAAS of a mixed meal and whole-body protein net balance has yet to be verified in this population.

Based on current research investigating whole-body protein kinetics, we hypothesize that higher-quality proteins (DIAAS $\geq 100\%$) elicit larger changes in whole-body protein balance compared to stepwise lower-quality proteins (i.e., DIAAS: 75% and 50%) and this follows the first limiting amino acid as all IAAs are required for synthesising new proteins.

10 OBJECTIVES OF THE STUDY

10.1 Primary objective

To determine the relationship between stepwise increases in DIAAS (protein quality) derived from modifications to combinatorial proteins within a whole-foods matrix and whole-body protein kinetics (PS + PB = NB) as a metric for lean tissue mass homeostasis in older adults.

10.2 Primary outcome

Post-prandial PS, PB, and NB responses.

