16.3 Visit 1 (day 1)

It will comprise the completion of the first arm of the test protocol.

- Participants will report to the lab/clinic after an overnight fast between 7-9:00h.
 - The lab environment will be air-conditioned at 21-22°C.
 - Each participant will report at a consistent time across the study to account for circadian variability.
 - The stable isotope infusion protocol will last for 5.5 hours, during which participants will remain in a semi-supine or seated position. A calibrated syringe infusion pump will administer a primed-constant continuous infusion of stable isotopes via a catheter inserted into the antecubital vein in one arm and a second catheter will be inserted in a collateral dorsal hand vein to obtain arterialized-venous blood samples following the positioning of the hand in a customized heated-hand box (overview 16.5). The primary outcome measure for this study will be the determination of net whole-body protein balance, which will be assessed using the stable isotopes L-[Ring-²H₅]-Phenylalanine and L-[Ring-²H₂]-Tyrosine. Infusion rates for L-[Ring-²H₅]-Phenylalanine and L-[Ring-²H₂]-Tyrosine will be 270 μmol/h⁻¹ and 85.5 μmol/h⁻¹, respectively, with priming doses of 270 μmol and 85.5 μmol. To prime the phenylalanine-derived plasma tyrosine pool, a bolus dose of L-[Ring-²H₄]-tyrosine will be administered (prime = 23.25 μmol) (Jonker et al., 2014; Jonker et al., 2019). To measure splanchnic extraction, each meal will include oral ingestion of 84 mg of L-[¹⁵N]-Phenylalanine (half about halfway through meal and the rest at the end of the meal co-ingested with the juice). During the study at time point 0 minutes (preprandial), 30, 90, and 240 minutes (postprandial) the participants will be asked about sensory information in response to the meal on a 10 cm Likert scale. Participants are allowed 133 ml/hour if male, and 115 ml/hour if female during the 5.5-hour infusion period (Yamada et al., 2022).
-

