18.2 Sample size calculations

The sample size was determined from the only relevant available NB data of Kim et al., 2018 where the egg vs. cereal difference (expected effect size between no and excellent quality) was 7 g net protein accretion in 165 min of infusion time, and the standard error derived from the p-value of 1.53 g (Kim et al., 2018). With the smallest important change of 2.2 g protein, using traditional null hypothesis significance testing with 5% type-1 and 20% type-2 error rates, a sample size of 8 was required (Hopkins, 2006), which we felt provided sufficient precision for the 30% of the anticipated difference between high and excellent protein quality, relative to the no quality contrast.

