18.6 Statistical analysis

18.6.1 Primary analysis

Outcomes will be analysed using a mixed model analysis of variance. Fixed effects will be meal condition and time (where relevant). The random effect will be subject to an unstructured covariance matrix to account for correlated data within the crossover. Data will be log-transformed to improve linearity and model fit and to express outcomes as percent differences. Primary outcomes (PS, PD, and NB) will be referenced to our estimate of the smallest important clinical changes. Data will be presented as the least-squares mean and uncertainty (95% confidence interval) and, where useful, the effect size as a standardized mean difference.

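### The protocol contradicts itself on its primary outcome: some sections name three outcomes, others net balance alone, and the trial was sized on net balance only

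*Protocol*

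**What the plan says.** Three places in the protocol make three outcomes primary:

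- Section 10.2: "Post-prandial PS, PB, and NB responses".
- Section 18.6.1: "Primary outcomes (PS, PD, and NB) will be referenced to our estimate of the smallest important clinical changes". PD here is the same quantity as PB; the abbreviation list explains protein degradation as breakdown.
- Synopsis, body text: "Primary outcomes (PS, PB, and NB) will be referenced to our estimate of the smallest important clinical changes".

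Two places make net balance the primary outcome:

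- Section 16.3: "The primary outcome measure for this study will be the determination of net whole-body protein balance".
- Synopsis, closing sentence, on what the results will be used for: "the primary health outcome of whole-body protein net balance governing lean mass homeostasis in older adults".

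The rest of the design points to net balance. The hypothesis at the end of section 9 predicts a larger change in whole-body protein balance for the highest-quality meal than for the 75% and 50% meals. Section 18.2 says "The sample size was determined from the only relevant available NB data", and gives 2.2 g as the smallest important change, with 5% type-1 and 20% type-2 error. No such figure is given for PS or PB.

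On comparisons, the synopsis says "The study will compare 3 dietary protein interventions increasing in the DIAAS". Section 18.6.1 specifies a mixed model with meal as a fixed effect and 95% confidence intervals. It lists no contrasts, and neither adopts nor rules out an adjustment for multiple comparisons.

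**The concern.** A trial with 8 participants and a disputed primary outcome leaves room to choose the headline after the data are seen. If NB were unclear and PS differed between two meals, the authors could cite 10.2 and report PS as a primary result. If the reverse happened, they could cite 16.3. A statistical analysis plan cannot settle this by itself, because following one section would mean departing from another.

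The error rates are also at stake. The 5% and 20% in section 18.2 were worked out for NB. They do not carry over to a claim that could rest on any of three outcomes.

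**Working it through.** **1. The protocol's own figure.** Inputs from 18.2: difference 2.2 g, variability 1.53 g, 5% type-1 error (two-sided assumed; sidedness is not stated), 80% power.

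n = 2 × ((1.960 + 0.842) × 1.53 / 2.2)² = 7.6, rounded up to 8.

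The stated n = 8 is reproduced, from NB data only. This reading uses 1.53 g as a within-subject SD, although 18.2 calls it a standard error; that is a separate matter. An exact paired-t version of the same reading gives 10.

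**2. What a correction would cost.** With the same formula, power to detect 2.2 g at n = 8 and the n needed for 80% power are:

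| Two-sided level per test | Power at n = 8 | n for 80% |
|---|---|---|
| 0.05 (one NB test) | 82% | 8 |
| 0.05/3 | 68.5% | 11 |
| 0.05/9 | 54% | 13 |

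Sections 11.2 and 16.1 cap recruitment at 8 plus 2 replacements, so 11 or 13 completers are out of reach.

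**3. False positives if all three outcomes are primary.** Three meals give three pairs, and three outcomes by three pairs give nine tests. Treated as independent, 1 − 0.95⁹ = 37.0%. That is too high, because NB is PS minus PB (synopsis) and the contrasts overlap. The chance was therefore simulated: n = 8, three periods, no meal effect on any outcome, NB = PS − PB exactly, each test two-sided at 5%, and 40,000 to 60,000 trials per setting. The protocol gives neither the within-subject PS-PB correlation nor the ratio of their SDs, so both are assumed. Each cell gives the chance of at least one false positive, with pooled error first and separate paired t tests second:

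| SD of PB / SD of PS | Correlation | Nine tests | Two hypothesis contrasts × three outcomes | Three NB contrasts only |
|---|---|---|---|---|
| 1 | 0 | 25.8% / 28.8% | 20.4% / 21.6% | 11.7% / 12.8% |
| 1 | 0.5 | 27.2% / 30.3% | 21.4% / 22.8% | 11.6% / 12.8% |
| 1 | 0.9 | 25.1% / 28.0% | 19.8% / 20.9% | 11.8% / 12.9% |
| 0.5 | 0 | 25.1% / 27.7% | 19.6% / 20.7% | 11.7% / 12.6% |
| 0.5 | 0.5 | 25.5% / 28.2% | 20.1% / 21.1% | 11.8% / 12.8% |
| 0.5 | 0.9 | 19.6% / 22.4% | 15.3% / 16.5% | 11.4% / 12.6% |

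Over all settings tried (correlation −0.5 to 0.95), nine tests give 18-27% with pooled error and 20-30% with paired tests. One overall three-meal test per outcome gives 8-13%.

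**4. With NB as the only primary outcome.** Three unadjusted NB contrasts still give 11-13%. If they are examined only after a significant three-meal test, the figure is about 5%. A single named NB contrast is held at 5% by construction.

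**The case against.** The strongest reply is that the protocol never says nine tests will be run. Section 18.6.1 gives no contrast list and no decision on adjustment, and both are commonly left to an analysis plan that is not shown here. That stands: the absence of an adjustment rule is not itself a fault of this document. The hypothesis compares the highest-quality meal with each of the two lower ones, so two contrasts per outcome have at least as much textual support as three.

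Second, the 5% in 18.2 is an input to a sample-size calculation, not a promise of error control across a family of tests. Section 18.6.1 describes estimation with intervals read against a smallest important change, with no rule that any significant result counts as success. This also stands. It limits the argument to the point that 5% would not describe a claim drawn from several outcomes.

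Third, a reader might infer that entering meal as an unordered factor is wrong because the hypothesis is ordered. The documents do not support that. A trend can be estimated from a three-level factor. Section 9 also expects no further gain once the limiting amino acid requirement is met, which a straight line on DIAAS would not represent.

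None of these replies touches the contradiction over which outcome is primary.

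**Conclusion.** The contradiction holds on the text alone: section 10.2, section 18.6.1 and the body of the synopsis cannot be reconciled with section 16.3 and the closing sentence of the synopsis. The hypothesis and sizing favour net balance.

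The size of the consequence is conditional. It is roughly 20-30% if all three outcomes are primary and all meal pairs are tested at an unadjusted 5%, and about 15-23% with the two hypothesis contrasts per outcome. Both ranges rest on an assumed PS-PB correlation and SD ratio; the lowest values arise when PB varies half as much as PS and the two are highly correlated. Every three-outcome scenario examined exceeds 5%.

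A reader might infer that the protocol commits to nine unadjusted tests, with a false-positive rate of 25-30% as a fixed property. It does not. The contrast set is open, and that narrower range needs common assumptions such as similar SDs for PS and PB.

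**What to change.** In sections 10.2, 16.3, 18.6.1 and the synopsis, name post-prandial NB over 0-240 min as the single primary outcome. List PS and PB as supportive outcomes, estimated with 95% confidence intervals.

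Name one primary NB contrast, CP1 versus CP3, at two-sided 5%. It sets excellent against no quality, the comparison for which 18.2 took its 7 g prior difference. Test the other two contrasts only after it, under a pre-stated order or adjustment. That choice needs thought. Section 18.2 anticipates the high-versus-excellent difference at 30% of the no-quality contrast, so CP1 versus CP2 would be about 0.30 × 7 = 2.1 g. If effects add, CP2 versus CP3 would be about 7 − 2.1 = 4.9 g. A fixed order that puts CP1 versus CP2 second could therefore stop before the larger difference is tested.

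The cost is wording in four places and loss of primary status for PS and PB. The sample size does not change on this account. A slope on DIAAS is optional and not part of this correction.

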10.3 Secondary objectives

To validate DIAAS as a metric of bioavailability of key and limiting amino acids in the plasma following meal ingestion from analysis of total plasma IAA, leucine, and lysine concentrations and total 4-h post-prandial AUC. To study the glycemic response to meals as a measure of health index and the insulin response as part of the mechanisms driving PS.

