10.4 Secondary outcomes

Post-prandial plasma:

1. AUC for total IAA concentration
2. AUC leucine (anabolic trigger for protein synthesis)
3. AUC lysine (first limiting amino acid)
4. Insulin
5. Glucose

Sensory analysis in response to the meals using linear Likert scales postprandial. This will be measured at 0 minutes preprandial and 30, 90, and 240 minutes postprandial.

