13 STUDY INTERVENTION

13.1 Study intervention description

The intervention combinatorial proteins (CP) meals will comprise three isocaloric (810 kcal) and isonitrogenous (22g protein) with stepwise increases in DIAAS (DIAAS: 50%, 75%, and 100%). Intervention foods will be commercially bought and stored at the lab location. An in-depth overview of the macronutrient and caloric composition of the three meals is shown in Table 1.

- CP1: Chickpeas, Quinoa, Quorn, and Bread (DIAAS 105%)
- CP2: Chickpeas, Quinoa, Tofu, and Bread (DIAAS 75%)
- CP3: Chickpeas, Quinoa, and Bread (DIAAS 50%)

	CP1	CP2	CP3
Bread, g	62	147	230
Chickpeas, g	30	44	54
Quinoa, g	55	22	23
Quorn, g	104		
Tofu, g		26	
DIAAS, %	105	75	50
First limiting amino acid	Lysine	Lysine	Lysine
Protein, g	22	21	22
Protein, kcal	88	84	88
Ingested IAA, g	9	9	9
Digested IAA, g	8	8	8
Ingested Leu, g	1.6	1.6	1.6
Digested Leu, g	1.5	1.5	1.5
Ingested Lys, g	1.2	0.9	0.7
Digested Lys, g	1.1	0.8	0.5
Carbohydrates, g	131	132	131
Carbohydrates, kcal	524	528	524
Fats, g	22	22	22
Fats, kcal	198	198	198
Fiber, g	13	7	9
Total kcal	810	810	810

Table 1: An overview of the macronutrient and caloric composition for the intervention meals with an overview of ingested and bioavailable IAAs, Leu (leucine), and Lys (lysine).

13.1.1 *Composition*

The macronutrient composition of each meal will consist of ~810 kcal using juice (carbohydrates) and olive oil (fats) to balance the macronutrient profiles (amounts need is shown in Table 2). The macronutrient profile will be ~11% protein, ~65% carbohydrates, and ~24% fats, as recommended by the Institute of Medicine (Manore, 2005). All interventional meals will contain 6-13g of fiber which is within normal per-meal fiber range (Table 1).

CP1: Chickpeas, Quinoa, Quorn, and Bread (DIAAS 105)		
Baker's Mango and Passionfruit juice	245	ml
Olive oil	15	ml
CP2: Chickpeas, Quinoa, Tofu, and Bread		
Baker's Mango and Passionfruit juice	140	ml
Olive oil	13	ml
CP3: Chickpeas, Quinoa, and Bread		
Baker's Mango and Passionfruit juice	7	ml
Olive oil	12	ml

Table 2: An overview of the number of juice (carbohydrates) and olive oil (fats) to balance the macronutrient profiles for every experimental meal to reach ~810 kcal.

Form and dosage

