18.6.2 Secondary analyses

The statistical analysis on secondary outcomes will be as for the primary, except sensory scale data will not be log-transformed.

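### The lysine AUC comparison cannot validate DIAAS as a bioavailability metric, because the lysine eaten falls with DIAAS across the three meals

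*Protocol*

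**What the plan says.** Section 10.3 (Secondary objectives) aims "To validate DIAAS as a metric of bioavailability of key and limiting amino acids in the plasma following meal ingestion", and names the data as coming "from analysis of total plasma IAA, leucine, and lysine concentrations and total 4-h post-prandial AUC". Section 10.4 lists the AUCs of total IAA, leucine and lysine as secondary outcomes and labels lysine as first limiting.

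Table 1 in Section 13.1 gives, in the order CP1, CP2, CP3:
- "DIAAS, % 105 75 50"
- "Ingested Lys, g 1.2 0.9 0.7"
- "Digested Lys, g 1.1 0.8 0.5"
- "Ingested Leu, g 1.6 1.6 1.6", with digested leucine 1.5 g in every meal
- total IAA 9 g ingested and 8 g digested in every meal; protein 22, 21 and 22 g

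On analysis, Section 18.6.2 states: "The statistical analysis on secondary outcomes will be as for the primary", apart from leaving the sensory scales unlogged. Section 18.6.1 fixes that model: a mixed model on log-transformed data with meal condition and, where relevant, time as fixed effects, reported as least-squares means with 95% confidence intervals. Nothing in the protocol adjusts for the lysine eaten, expresses AUC per gram of lysine, or sets the observed ratios against a predicted ratio. The oral tracer in Section 16.3 is labelled phenylalanine, given to measure splanchnic extraction; it does not trace lysine.

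**The concern.** A claim that DIAAS measures bioavailability is a claim about what happens between the plate and the plasma. DIAAS multiplies the content of the limiting amino acid by its ileal digestibility, and Section 9 presents digestibility as the basis of the score. To support a bioavailability claim, the data would have to tell two accounts apart: plasma lysine follows digestible lysine, or it simply follows lysine eaten.

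The three meals do not allow this. Leucine and total IAA are matched, both ingested and digested, so their AUCs are not expected to move with DIAAS. Lysine does move, but its intake moves in the same order and by most of the same amount. A score with no digestibility term would rank the meals identically.

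At stake is the conclusion attached to this objective. A clear stepwise fall in lysine AUC would be easy to report as validation of DIAAS, when it may show only that participants ate less lysine.

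**Working it through.** **Inputs (Table 1, Section 13.1; CP1, CP2, CP3).** Ingested lysine 1.2, 0.9, 0.7 g. Digested lysine 1.1, 0.8, 0.5 g. DIAAS 105, 75, 50%. Protein 22, 21, 22 g. Completers: 8 (Section 18.2). The protocol gives no variance for lysine AUC.

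**Step 1. Does Table 1 hang together?** Digested lysine per gram of protein is 1100/22 = 50.0, 800/21 = 38.1 and 500/22 = 22.7 mg/g. Dividing by DIAAS gives an implied reference of 47.6, 50.8 and 45.5 mg/g. With lysine rounded to 0.1 g and protein to 1 g, the ranges are 44.4–50.9, 46.5–55.3 and 40.0–51.2. They share 46.5–50.9, so the table is consistent with a single reference value.

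**Step 2. Implied lysine digestibility.** 1.1/1.2 = 0.92, 0.8/0.9 = 0.89, 0.5/0.7 = 0.71. On the rounded figures only CP3 stands apart.

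**Step 3. What each account predicts for AUC relative to CP1, if AUC is proportional to supply.**

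| | CP2:CP1 | CP3:CP1 |
|---|---|---|
| Content only | 0.9/1.2 = 0.75 | 0.7/1.2 = 0.58 |
| Digested lysine | 0.8/1.1 = 0.73 | 0.5/1.1 = 0.45 |
| DIAAS | 75/105 = 0.71 | 50/105 = 0.48 |

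**Step 4. Ingested lysine against DIAAS.** Deviations from the mean are 0.267, −0.033, −0.233 g and 28.33, −1.67, −26.67 points. r = 13.833 / √(0.12667 × 1516.67) = 0.998. For digested lysine r = 0.999. Three points make any correlation a description only, but the two predictors clearly cannot be told apart.

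**Step 5. Share of the log difference in digested lysine that content supplies** = ln(ingested ratio) / ln(digested ratio).
- CP1–CP3: ln(1.2/0.7) / ln(1.1/0.5) = 0.539/0.788 = 68%
- CP1–CP2: ln(1.2/0.9) / ln(1.1/0.8) = 0.288/0.318 = 90%
- CP2–CP3: ln(0.9/0.7) / ln(0.8/0.5) = 0.251/0.470 = 53%

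**Step 6. Rounding.** Moving each lysine figure by ±0.05 g, the CP1–CP3 share runs from ln(1.15/0.75) / ln(1.15/0.45) = 46% to ln(1.25/0.65) / ln(1.05/0.55) = 101%. The CP3:CP1 digestibility ratio, 0.714/0.917 = 0.78, could lie between 0.60 and 1.01. Table 1 as printed therefore does not exclude that digestibility contributes nothing to the CP1–CP3 contrast.

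**Step 7. Would content alone produce a meal difference with 8 participants?** Assume log AUC has mean ln(ingested lysine), and use the meal F test on 2 and 14 df. The non-centrality is λ = 8 × Σ(mᵢ − m̄)² / ln(1 + CV²) = 8 × 0.1455 / ln(1 + CV²). The within-person CVs are assumed.

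| CV | λ | Probability of rejecting equal AUC |
|---|---|---|
| 20% | 29.7 | 99.5% |
| 30% | 13.5 | 85% |
| 40% | 7.8 | 61% |

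If AUC rises only with the square root of the lysine eaten, the figures are 58% at a 20% CV and 30% at 30%. A meal effect is thus quite likely without any difference in digestibility.

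**Step 8. Does dividing AUC by lysine ingested cure this?** That is a log offset, which fixes the dose slope k at 1. If AUC in fact varies as supply to the power k:
- digested lysine drives AUC, k = 0.7: adjusted CP3:CP1 = 0.4545^0.7 / 0.5833 = 0.99, which reads as content only
- digested lysine drives AUC, k = 0.5: 0.4545^0.5 / 0.5833 = 1.16, the wrong side of 1
- content only, k = 0.5: 0.5833^0.5 / 0.5833 = 1.31, and the adjusted test rejects 58% of the time at a 20% CV

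Three fixed meals give no independent estimate of k.

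**The case against.** The best defence is that DIAAS includes content by definition. Lowering lysine while holding protein, total IAA and leucine steady is the deliberate manipulation, and Section 10.3 can be read as asking only whether plasma lysine tracks the score. On that reading a content difference is the signal. This stands in part: the design is coherent as a test of digestible lysine supply. It does not stand for bioavailability, which is the word the objective uses.

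A reader might go further and infer that the planned test has an inflated type-1 error, taking the 99.5%, 85% and 61% in Step 7 against a nominal 5%. The protocol does not support that. If intake differs and AUC follows it, equal AUC is false, so these figures are power against a true supply difference. They also rest on assumed CVs and assumed proportionality.

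A reader might also infer that a significant lysine contrast is the protocol's validation rule. No section says so. The planned estimates and intervals could be set against predicted ratios, and a criterion could sit in a statistical analysis plan that is not shown. What remains is a mismatch inside the protocol: no criterion applied to these three meals alone would separate digestibility from content without an untestable assumption about dose response.

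Finally, one might want lysine AUC per gram ingested to become the validation test. Step 8 shows why it should not.

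**Conclusion.** The point holds as a limit on what may be concluded. With total IAA and leucine matched and lysine intake falling 1.2, 0.9, 0.7 g, a meal difference in lysine AUC shows a higher lysine supply. It cannot validate DIAAS as a bioavailability metric over plain lysine content. Content supplies about 68% of the log CP1–CP3 difference in digested lysine (about 46% to 101% with rounding) and, on the printed figures, about 90% of CP1–CP2.

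The shares come from Table 1 alone. Turning them into predicted AUC ratios assumes that AUC is proportional to supply. The protocol does not establish this for a baseline-referenced 4-hour plasma AUC.

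The scope is one secondary objective. The primary outcomes (protein synthesis, breakdown and net balance) and the sample size are not affected.

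**What to change.** 1. In Section 10.3, restate the objective as describing whether plasma lysine AUC follows the digestible lysine supply that DIAAS predicts.
2. In Sections 10.3 and 18.6.2, state that a meal difference in lysine AUC alone does not validate DIAAS as a bioavailability metric over lysine content.
3. In Section 18.6.2, report the CP3:CP1 and CP2:CP1 lysine AUC ratios with 95% CIs beside both predictions: content only (0.58 and 0.75 from Table 1) and digested lysine (0.45 and 0.73). Recompute all four from the unrounded meal values.
4. If AUC per gram of lysine ingested is shown, label it a sensitivity analysis and state that it assumes AUC proportional to dose, which three fixed meals cannot check.

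The model, visits, samples and participants are unchanged. The work is a wording amendment and two sets of reference ratios. The cost is a weaker secondary claim: the trial can describe agreement with predicted lysine supply but cannot announce a validation of DIAAS from these data.
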